9.3. Clinical Laboratory Tests

9.3.1. Laboratory Value Definitions

All laboratory assessments will be performed using a central laboratory with the exception of urine pregnancy tests. Laboratory values and change from baseline values will be summarized descriptively by visit; non-numeric test values will be tabulated when necessary. Baseline will be determined according to Section 4.1.3, using the last nonmissing value collected before the first application, prioritizing scheduled assessments for baseline identification over unscheduled visits. The last record before application in the highest priority will be considered the baseline record. For baseline laboratory candidates with the same date and time in the same priority category, additional rules may be provided after consultation with the medical monitor to delineate which value will be defined as baseline.

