^a Visits at Weeks 2, 4, 8, 12, 18, 20, 24, and 28 can be performed virtually (through telemedicine if applicable) only due to COVID-19-related reasons. No efficacy assessments can be performed virtually (see [Appendix B](#)).

^b All Week 16 assessments must be completed before the participant can continue in the OLE period. Study drug will not be applied in the clinic at Week 16 for participants not continuing into the OLE period.

^c Participants who withdraw from the study early should complete the ET and the safety follow-up visits.

^d Targeted physical examinations can be performed for assessment of AEs and during other visits, including unscheduled visits, as per discretion of the investigator.

^e The total %BSA affected should be \leq 20% to be eligible for study entry and continued participation.

^f Target lesions typical of LP (3 or more) will be identified at baseline.

^h Not necessary if screening assessment is performed within 14 days of Day 1.

ⁱ Laboratory assessments are optional during unscheduled visits based on investigator's discretion and clinical judgment.

^j Women of nonchildbearing potential only. FSH is not needed in women with documented hysterectomy, bilateral salpingectomy, or bilateral oophorectomy.

^k Female participants of childbearing potential will have a serum test at screening, a urine pregnancy test before Day 1 study cream application, and a urine test at other visits noted. A positive urine test must be confirmed by a serum test.

[REDACTED]

[REDACTED]

[REDACTED]

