8.1.2. Screening Procedures

Screening is the interval between signing the ICF and the day the participant is enrolled in the study (Day 1). Screening may not exceed 28 days. Assessments that are required to demonstrate eligibility may be performed over the course of 1 or more days during the screening process.

Procedures conducted as part of the participant's routine clinical management (eg, blood counts or physical examinations) and obtained before signing of the ICF may be used for screening or baseline purposes provided that the procedure meets the Protocol-defined criteria and has been performed in the timeframe of the study (ie, within 28 days or less prior to Day 1). For participants who are enrolled in the study, information associated with eligibility requirements must be entered into the appropriate eCRF pages.

Results from the screening visit evaluations will be reviewed to confirm eligibility before randomization and the administration of study drug. Tests with results that fail eligibility requirements may be repeated once during screening if the investigator believes the results to be in error. For screening assessments that are repeated, the most recent available result before randomization will be used to determine eligibility.

See Sections [5.4](#) and [5.5](#) for information regarding screen failures and replacement of participants, respectively.

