4.1.3. Baseline Value

Baseline is the last nonmissing measurement obtained before or on the day of the first application of ruxolitinib cream or vehicle cream for the DBVC period.

For randomized participants not treated with any study drug, baseline is defined as the last nonmissing assessment before randomization for all parameters.

For participants who continue in the OLE period, baseline is defined as follows:

- For efficacy evaluation in the OLE period, baseline is the last nonmissing measurement obtained before or on the day of first application of study treatment in the DBVC period.
- For safety evaluation in the OLE period:
 - For participants who cross over from vehicle group to ruxolitinib cream, the baseline is the last nonmissing measurement obtained before or on the day of first application of ruxolitinib cream in the OLE period.
 - For participants who apply ruxolitinib cream in both periods, baseline is the last nonmissing measurement obtained before or on the day of first application of study treatment in the DBVC period.

When a scheduled assessment and an unscheduled assessment occur on the same day and the times of the assessments are not available, use the following convention to determine baseline:

- If both a scheduled and an unscheduled visit are available on the day of the first dose and the time is missing, use the scheduled assessment as baseline.
- If all scheduled assessments are missing on the day of the first application, but an unscheduled assessment is available, use the unscheduled assessment as baseline.

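### SAP 9.3.1 and SAP 4.1.3 give conflicting laboratory baseline rules; read literally, 9.3.1 can make a superseded failing screening value the baseline when the repeat is labelled unscheduled and the Day 1 draw is waived

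*SAP*

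**What the plan says.** **General rule, SAP 4.1.3.** "Baseline is the last nonmissing measurement obtained before or on the day of the first application of ruxolitinib cream or vehicle cream". Visit type matters only when a scheduled and an unscheduled assessment fall on the same day and their times are not available; the scheduled one is then used.

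**Laboratory rule, SAP 9.3.1.** It starts from the general rule: "Baseline will be determined according to Section 4.1.3, using the last nonmissing value collected before the first application". It then continues: "prioritizing scheduled assessments for baseline identification over unscheduled visits. The last record before application in the highest priority will be considered the baseline record". No same-day condition is attached. The next sentence deals separately with candidates that share a date, a time and a priority category.

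**Repeats, Protocol 5.4 and 8.1.2.** A screening test that fails an eligibility limit may be repeated once, and "the most recent available result before randomization will be used to determine eligibility".

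**Day 1 draw, Protocol Table 3.** Chemistry and hematology are scheduled at screening and on Day 1. Footnote h says of the Day 1 draw: "Not necessary if screening assessment is performed within 14 days of Day 1".

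Neither document says whether a repeated screening test is stored as a scheduled screening record or as an unscheduled one.

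**The concern.** Section 9.3.1 claims to follow 4.1.3 but gives a different answer for records on different dates. A programmer who follows 4.1.3 sorts by date. One who follows the added wording of 9.3.1 sorts by visit type first and by date within type. Both could say that they followed the SAP.

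The difference matters most for repeated screening tests. A test is repeated because the first result was on the wrong side of an eligibility limit, and the participant enters because the second was on the right side. If the first is kept as baseline, the baseline for that analyte is worse than the value used for eligibility, so later deterioration looks smaller. The outputs exposed are those measured against baseline in SAP 9.3.1 and 9.3.2: change from baseline, the normal-range shift table, the CTCAE grade shift table and the count of participants whose abnormalities worsened. The baseline laboratory summary could also show a value that meets an exclusion criterion in a participant who was correctly enrolled.

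**Working it through.** The plan states no figure on this point, so there is none to reproduce. The check applies both rules to the same records.

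**Rules as coded**
- 9.3.1, literal: take the scheduled records if there are any, otherwise the unscheduled ones; choose the latest within that class.
- 4.1.3: choose the latest date; if a scheduled and an unscheduled record share it, choose the scheduled one.
- Change = on-treatment value minus baseline.

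**Inputs.** The hemoglobin eligibility limit (below 100 g/L excludes) is from Protocol 5.2, criterion 3a. The dates and hemoglobin values are assumed for illustration: failed test 97, repeat 104, Day 1 value 103 where drawn, on-treatment value 96 or 98 g/L.

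| Case | Records before first application | Baseline, 9.3.1 | Baseline, 4.1.3 |
|---|---|---|---|
| A | Scheduled Day -12: 97; unscheduled Day -5: 104; Day 1 waived | 97 | 104 |
| B | Scheduled Day -25: 97; unscheduled Day -18: 104; Day 1 drawn: 103 | 103 | 103 |
| C | Scheduled Day -12: 97; repeat on Day -5 stored as scheduled: 104; Day 1 waived | 104 | 104 |
| D | Scheduled Day -25: 97; unscheduled Day -5: 104; Day 1 waived because of the repeat | 97 | 104 |

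**Changes**
- A and D under 9.3.1: 96 - 97 = -1 and 98 - 97 = +1 g/L. There is no new value below 100, because the baseline is already below it.
- A and D under 4.1.3: 96 - 104 = -8 and 98 - 104 = -6 g/L, each a new value below 100.
- B, both rules: 96 - 103 = -7 and 98 - 103 = -5 g/L.
- C, both rules: 96 - 104 = -8 and 98 - 104 = -6 g/L.

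The gap between the rules in A and D is 104 - 97 = 7 g/L, which is simply the distance between the two screening values.

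**What the cases show.** The rules part only when the Day 1 draw is absent and the repeat is unscheduled. Case A does not depend on how footnote h is read, since the scheduled screening draw is itself within 14 days. Case D needs the repeat to count as the screening assessment for the waiver while still being labelled unscheduled, which is a less natural combination.

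**Carry-over into the open-label period.** Under SAP 4.1.3, participants on ruxolitinib in both periods keep their double-blind baseline for safety, so an affected value would stay with them. Participants crossing from vehicle get a new safety baseline at first ruxolitinib application, and laboratory tests are scheduled at Week 16, so their open-label summaries would normally be unaffected.

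**The case against.** The strongest reply is that the problem may never arise. Table 3 schedules a Day 1 draw, and footnote h makes it unnecessary without forbidding it. Protocol 8.1.4 places clinic application after the safety blood draws, so a Day 1 value would be the baseline under both rules. Protocol 8.1.2 treats a repeat as a screening assessment and allows screening to run over more than one day, while Protocol 8.6 describes unscheduled visits without mentioning screening repeats. A repeat stored as a screening record gives case C, with no conflict. A full rescreen under a new participant number (Protocol 5.4) also gives fresh scheduled records. All of this stands, and it is why the effect is conditional.

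A second reply is that 9.3.1 names 4.1.3 and the last nonmissing value, so scheduled-first was perhaps meant only as the same-day tie-break. That may be the intent. The text does not say so, and the sentence on candidates with the same date and time in one category treats category as something separate from date. The conflict therefore remains.

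A reader might go further and infer that the rule conceals deterioration. The documents do not support that. By-visit values do not use this baseline. Abnormal hematology and chemistry values are listed (Listings 2.8.1.4 and 2.8.1.5), and clinically meaningful results are reported as adverse events under Protocol 9.1. Laboratory data are descriptive, with no formal comparison between groups (Protocol 10.4.3), and the double-blind baseline rule is the same in both arms.

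A reader might also take the change from the repeat as the true change. That is not supported either: the repeat was accepted because it passed, so chance variation may have raised it just as it may have lowered the first value. The case for the repeat is that it is later, nearer to treatment and the value on which eligibility rested.

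**Conclusion.** The conflict between SAP 9.3.1 and SAP 4.1.3 is real and visible in the text. Read literally, 9.3.1 makes a superseded failing value the baseline if three things coincide: a failed screening test is repeated, the repeat is recorded as unscheduled, and the Day 1 draw is not taken. For the failed analyte the error has one direction, so baseline-relative summaries understate worsening by the distance between the two screening values (7 g/L in the assumed example).

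The number of participants affected cannot be derived. The documents give no rate of failed and repeated tests, of Day 1 waivers or of unscheduled labelling, and zero is possible. The 100 g/L limit in the example is an eligibility criterion and is not put forward as a boundary in any planned shift table.

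The primary endpoint, the other efficacy analyses and every hypothesis test are untouched. This is a modest correction to the safety analysis, worth making because the choice of baseline should not depend on which sentence is programmed.

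**What to change.** In SAP 9.3.1:

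1. Select the laboratory baseline by date, as in 4.1.3: the last nonmissing value before first application, including a qualifying screening repeat whatever its visit label.
2. Limit the preference for scheduled records to same-day records without times.
3. Reword the next sentence, on ties within a priority category, to match. Deleting the priority wording alone would leave that sentence referring to categories that no longer exist.
4. Use one time limit in both sections. At present 4.1.3 admits values from the day of first application, while 9.3.1 says before the application.

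The cost is a few sentences in the SAP and a matching change in the derivation program, best made before laboratory baselines are derived. No new data are needed, and no visit or procedure changes.

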9.3.2. Laboratory Value Summaries

All test results and associated normal ranges from central laboratories will be reported in SI units. All tests with numeric values will have a unique unit per test. Any laboratory test results and associated normal ranges from local laboratories will be converted to SI units.

When there are multiple laboratory nonmissing values for a participant's particular test at a scheduled visit, central laboratory values have higher priority over local laboratory values. If a tie still exists, the laboratory value with the smallest laboratory sequence number will be used in by-visit summaries.

For test results that will be summarized with available normal ranges, the number and percentage of participants with the laboratory values being low (but never high), normal, high (but never low), and both low and high will be calculated for each test. A shift summary will be produced for each test. The denominator for the percentage calculation will use the number of participants in the baseline category (ie, low, high, normal, or missing) as the denominator for the percentage in each of the categories during the study.

Severity grades will be assigned to laboratory test values based on the numerical component of CTCAE v5. Shift tables will also be presented showing change in CTCAE grade from baseline to the worst grade postbaseline. Separate summaries for abnormally high and abnormally low laboratory values will be provided when the laboratory parameter has both high and low grading criteria. The denominator for the percentage calculation will be the number of participants in the baseline category. The number of participants who experienced worsening of laboratory abnormalities will be summarized by maximum severity.

9.4. Vital Signs

Values at each scheduled visit, change, and percentage change from baseline for vital signs, including systolic blood pressure, diastolic blood pressure, pulse, temperature, and respiratory rate will be summarized descriptively.

Normal ranges for vital sign values are defined in [Table 4](#). For participants exhibiting vital sign abnormalities, the abnormal values will be listed along with their assigned treatment group. Alert vital signs are defined as an absolute value outside the defined normal range and percentage change greater than 25%. The abnormal values for participants exhibiting alert vital sign abnormalities will be listed.

Table 4: Criteria for Clinically Notable Vital Sign Abnormalities

Parameter	High Threshold	Low Threshold
Systolic blood pressure	> 155 mmHg	< 85 mmHg
Diastolic blood pressure	> 100 mmHg	< 40 mmHg
Pulse	> 100 bpm	< 45 bpm
Temperature	> 38°C	< 35.5°C
Respiratory rate	> 20 breaths/min	< 8 breaths/min

10. PLANNED ANALYSES

No formal interim analysis is planned in this study.

There are 2 formal planned analyses:

- The primary analysis will occur after the primary database lock, when all participants have completed the DBVC period. The sponsor will be unblinded after the primary database lock; however, investigators and participants will remain blinded to the individual study treatment assignment after the primary database lock.
- The final analysis will occur when all participants have completed or withdrawn from the study.

11. CHANGES AND MODIFICATIONS TO THE ANALYSIS PLAN

All versions of the SAP are listed in [Table 5](#).

Table 5: Statistical Analysis Plan Versions

SAP Version	Date
Original	30 AUG 2023

11.1. Changes to Protocol-Defined Analyses

11.2. Changes to the Statistical Analysis Plan

Not applicable.

APPENDIX A. PLANNED TABLES, FIGURES, AND LISTINGS

This appendix provides a list of the planned tables, figures, and listings for the Clinical Study Report. Shells are provided in a separate document for tables that are not in the most current Standard Safety Tables v1.13.

The lists of tables, figures, and listings are to be used as guidelines. Modifications of the lists that do not otherwise affect the nature of the analysis will not warrant an amendment to the SAP.

Tables

Table No.	Title	Population	Standard
Baseline and Demographics Characteristics			
1.1 Disposition			
1.1.1	Analysis Populations	ITT	X
1.1.2.1	Summary of Participant Disposition in the DBVC Period	ITT	X
1.1.2.2	Summary of Participant Disposition in the OLE Period	OLE	X
1.1.3	Summary of Number of Participants Enrolled by Country and Site	ITT	X
1.1.4.1	Summary of Protocol Deviations in the DBVC Period	ITT	X
1.1.4.2	Summary of Protocol Deviations in the OLE Period	OLE	X
1.2 Demographics and Baseline Characteristics			
1.2.1	Summary of Demographics and Baseline Characteristics in the DBVC Period	ITT	X
1.2.2	Summary of Demographics and Baseline Characteristics in the OLE Period	OLE	X
1.3 Baseline Disease Characteristics			
1.3.1	Summary of Baseline Disease Characteristics in the DBVC Period	ITT	X
1.3.2	Summary of Baseline Disease Characteristics in the OLE Period	OLE	X
1.4 Prior and Concomitant Medication			
1.4.1	Summary of Prior Medications in the DBVC Period	ITT	X
1.4.2.1	Summary of Concomitant Medications in the DBVC Period	ITT	X
1.4.2.2	Summary of Concomitant Medications in the OLE Period	OLE	X
1.5 Others			
1.5	Summary of General Medical History in the DBVC Period	ITT	X
Efficacy			
2.1 IGA Score			
2.1.1	Summary and Analysis of Participants Achieving IGA-TS in Treatment Periods	ITT	
2.1.2	Summary and Analysis of Participants Achieving IGA-TS by Sex in Treatment Periods	ITT	
2.1.3	Summary and Analysis of Participants Achieving IGA-TS by Categorical Age in Treatment Periods	ITT	
2.1.4	Summary and Analysis of Participants Achieving IGA-TS by Duration of Disease in Treatment Periods	ITT	

[figure not shown]
Table No.	Title	Population	Standard
3.1.1.3	Summary of Exposure in Treatment Periods	Safety	X
3.1.2.1	Summary of Study Drug Compliance in the DBVC Period	Safety	
3.2 Adverse Events			
3.2.1.x	Overall Summary of Treatment-Emergent Adverse Events	Safety	X
3.2.2.x	Summary of Treatment-Emergent Adverse Events by MedDRA System Organ Class and Preferred Term	Safety	X
3.2.3.x	Summary of Treatment-Emergent Adverse Events by MedDRA Preferred Term in Decreasing Order of Frequency	Safety	X
3.2.4.x	Summary of Treatment-Emergent Adverse Events by MedDRA System Organ Class, Preferred Term, and Maximum Severity	Safety	X
3.2.5.x	Summary of Treatment-Emergent Adverse Events by MedDRA System Organ Class, Preferred Term, and CTCAE Grade Category	Safety	
3.2.6.x	Summary of Grade 3 or Higher Treatment-Emergent Adverse Events by MedDRA System Organ Class and Preferred Term	Safety	X
3.2.7.x	Summary of Grade 3 or Higher Treatment-Emergent Adverse Events by MedDRA Preferred Term in Decreasing Order of Frequency	Safety	X
3.2.8.x	Summary of Serious Treatment-Emergent Adverse Events by MedDRA System Organ Class and Preferred Term	Safety	X
3.2.9.x	Summary of Serious Treatment-Emergent Adverse Events by MedDRA Preferred Term in Decreasing Order of Frequency	Safety	X
3.2.10.x	Summary of Treatment-Related Treatment-Emergent Adverse Events by MedDRA System Organ Class and Preferred Term	Safety	X
3.2.11.x	Summary of Treatment-Related Treatment-Emergent Adverse Events by MedDRA Preferred Term in Decreasing Order of Frequency	Safety	X
3.2.12.x	Summary of Grade 3 or Higher Treatment-Related Treatment-Emergent Adverse Events by MedDRA System Organ Class and Preferred Term	Safety	
3.2.13.x	Summary of Treatment-Related Serious Treatment-Emergent Adverse Events by MedDRA System Organ Class and Preferred Term	Safety	X
3.2.14.x	Summary of Treatment-Emergent Adverse Events With a Fatal Outcome by MedDRA System Organ Class and Preferred Term	Safety	X
3.2.16.x	Summary of Treatment-Emergent Adverse Events Leading to Dose Interruption by MedDRA System Organ Class and Preferred Term	Safety	X
3.2.17.x	Summary of Treatment-Emergent Adverse Events Leading to Discontinuation of Study Drug by MedDRA System Organ Class and Preferred Term	Safety	X
3.2.18.x	Summary of Application Site Reactions by MedDRA Preferred Term in Decreasing Order of Frequency	Safety	X
3.3 Laboratory			
3.3.1.1.x	Summary of Laboratory Values – Hematology	Safety	X
3.3.1.2.x	Summary of Laboratory Values – Chemistry	Safety	X
3.3.2.1.x	Shift Summary of Hematology Laboratory Values – to the Worst Abnormal Value	Safety	X
3.3.2.2.x	Shift Summary of Chemistry Laboratory Values – to the Worst Abnormal Value	Safety	X

Table No.	Title	Population	Standard
3.3.3.1.x	Shift Summary of Hematology Laboratory Values in CTCAE Grade – to the Worst Grade Abnormal Value	Safety	X
3.3.3.2.x	Shift Summary of Chemistry Laboratory Values in CTCAE Grade – to the Worst Grade Abnormal Value	Safety	X
3.4 Vital Signs			
3.4.1.x	Summary of Systolic Blood Pressure	Safety	X
3.4.2.x	Summary of Diastolic Blood Pressure	Safety	X
3.4.3.x	Summary of Pulse	Safety	X
3.4.4.x	Summary of Respiratory Rate	Safety	X
3.4.5.x	Summary of Body Temperature	Safety	X

Note: For AE tables ending with "x," separate tables will be provided for the DBVC period, OLE period, and the treatment periods (DBVC and OLE periods). For laboratory and vital sign tables ending with "x," separate tables will be provided for the DBVC period and the OLE period.

Figures

Figure No.	Title	Population
Efficacy		
4.1.1.1	Proportion of Participants Achieving IGA-TS in Treatment Periods	ITT
4.1.1.2	Proportion of Participants Achieving IGA-TS by Sex in Treatment Periods	ITT
4.1.1.3	Proportion of Participants Achieving IGA-TS by Baseline Age Group in Treatment Periods	ITT
4.1.1.4	Proportion of Participants Achieving IGA-TS by Baseline Duration of Disease in Treatment Periods	ITT
4.1.1.5	Proportion of Participants Achieving IGA-TS by Race in Treatment Periods	ITT
4.1.1.5	Forest Plot of Response Rate Difference in Achieving IGA-TS at Week 16	ITT
4.2.1.1	Proportion of Participants Achieving ITCH4 in Treatment Periods	ITT
4.2.2.1	Mean and Standard Error Plot of By-Visit Itch NRS Score in Treatment Periods	ITT
[REDACTED]	[REDACTED]	[REDACTED]
4.2.3.1	Mean and Standard Error Plot of Daily Itch NRS Score from Day 1 to Day 28	ITT
[REDACTED]	[REDACTED]	[REDACTED]
4.2.4	Kaplan-Meier Curve of Time to ITCH4 in the DBVC Period	ITT
4.3.1.1	Mean and Standard Error Plot of By-Visit Skin Pain NRS Score in Treatment Periods	ITT
[REDACTED]	[REDACTED]	[REDACTED]

Listings

Listing No.	Title
